3.3 Exploratory objectives

Correlate the level of expression of mTOR pathway signaling proteins in archival tumor tissue with the clinical activity of everolimus

Correlate the level of expression of somatostatin receptor expression and IGF1-R in archival tumor tissue with clinical efficacy of Pasireotide

Exploratory analysis of disease response based on histology and FDG PET uptake

4 Study design

This is an open-label, 3-arm, non comparative phase II clinical trial to study the single agent and combined efficacy of pasireotide and everolimus in patients with iodine refractory, differentiated (papillary, follicular and their variants) and medullary thyroid cancer. Patients will be randomly assigned to one of three arms to receive single agent pasireotide, everolimus or the combination of both drugs (Figure 4). Patient randomization will be stratified by histology, (medullary versus non medullary thyroid cancer). In order to explore the optimal schedule of administration,

patients who were initially randomized to the single agent arm will be allowed to receive the second agent at the time of disease progression. Such patients, however, may only proceed with the trial if they achieve disease stabilization or objective response at the end of the first 2 cycles of 2-drug combination and without experiencing any grade ≥ 4 hematologic or grade ≥ 3 non-hematologic toxicities. Everolimus will be administered once daily continuously on days 1 to 28; pasireotide will be administered as a long acting intramuscular depot injection given once every 4 weeks. One cycle will be defined as 4 weeks with response assessment with cross sectional imaging planned for the end of every even numbered cycle. Biochemical response will be assessed using serum-based tumor markers (Thyroglobulin, CEA, calcitonin) specific or informative for the histologic subtype of thyroid cancer. Patients will be evaluated at the end of cycle 1 and cycle 2, and subsequently after every 2 cycles along with restaging scans.

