4.2 Follow-up

Patients will remain on treatment and be followed at regularly scheduled office visit until treatment discontinuation due to progression, withdrawal of consent, or intolerable toxicity. Patients who discontinued therapy for reason of toxicity will be monitored at least monthly via phone or office visit until resolution of the adverse event. "All patients will be contacted for survival follow-up at least monthly via phone or office visit until death or the completion of the trial (LPLV + 30 days).

[figure not shown]

Figure 4-2: Flow diagram of the study schema, screening, stratification and randomization to one of 3 arms.

5 Population

Ninety adult patients with pathologically confirmed medullary or differentiated thyroid cancer who no longer benefit from or are intolerant of radioiodine therapy will be enrolled in the study. Patients will be enrolled across all participating sites in order of registration into the study. Patients who meet the eligibility and screening requirement will be stratified by histology, for the purposes of randomization to one of the 3 treatment arms. Patients will be randomly assigned to one of three treatment arm as described in the statistics section for a total of thirty patients in each arm.

Inclusion/exclusion criteria

The investigator or his/her designee must ensure that all patients who are offered enrollment in the study meet all of the following inclusion and exclusion criteria:

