7.4 Efficacy

Primary efficacy assessment

The primary endpoints of this study are response rate (RR) and progression free survival (PFS). Interim analysis for the RR primary endpoint will be performed after 18 evaluable patients have been enrolled for each arm of treatment. Any arm not meeting the pre-specified efficacy RR (specified in Section 10.1 under statistical analysis) will be closed to further accrual. Tumor response assessment will be performed after every two cycles of therapy using cross-sectional imaging according to the RECIST 1.1 criteria.

All patients who completed at least 2 cycles of therapy will be deemed evaluable for the efficacy endpoint. In the event of study discontinuation prior to completing two treatment cycles for reasons other than disease progression, the affected subject will be considered inevaluable for efficacy and will be replaced by another subject (comparable as per stratification criteria) to be enrolled on the same arm of the study.

Patients who discontinue treatment due to drug-related toxicity prior to obtaining a restaging scan would be considered inevaluable and would be replaced.

Patients who discontinue treatment for symptomatic disease progression prior to a restaging scan would be deemed to have progressed as of the time of treatment discontinuation and will not be replaced.

Patients who are lost to follow-up will be censored as of the last official contact date for efficacy and survival outcome analysis. If the event occurred prior to the first restaging scan such patients will be deemed inevaluable for RR efficacy endpoint and will therefore be replaced by another

patient. They will, however, remain evaluable for overall safety assessment provided they have received at least one dose of the study drug..

Secondary efficacy assessments

Assessment for other secondary and exploratory endpoint will be performed at study conclusion.

Patient will be evaluable for overall toxicity and safety endpoint determination if they received any dose of the investigational agent.

Any patient deemed inevaluable for efficacy assessment as a result of treatment discontinuation due to treatment-related toxicity may still be evaluated for overall safety profile assessment.

Notwithstanding this provision, however, only patients who are evaluable for the primary efficacy endpoint may be included in the safety assessment conducted for the sole of picking a winning arm for the trial.

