Evaluation of Target Lesions

- * Complete Response (CR): Disappearance of all target lesions
- * Partial Response (PR): At least a 30% decrease in the sum of the LD of target lesions, taking as reference the baseline sum LD
- * Progressive Disease (PD): At least a 20% increase in the sum of the LD of target lesions, taking as reference the smallest sum LD recorded since the treatment started or the appearance of one or more new lesions

* Stable Disease (SD): Neither sufficient shrinkage to qualify for PR nor sufficient increase to qualify for PD, taking as reference the smallest sum LD since the treatment started

Evaluation of Non-Target Lesions

* Complete Response (CR): Disappearance of all non-target lesions and normalization of tumor marker level

* Incomplete Response/Stable Disease (SD): Persistence of one or more non-target lesion(s) or/and maintenance of tumor marker level above the normal limits

* Progressive Disease (PD): Appearance of one or more new lesions and/or unequivocal progression of existing non-target lesions (1)

Although a clear progression of “non target” lesions only is exceptional, in such circumstances, the opinion of the treating physician should prevail and the progression status should be confirmed later on by the review panel (or study chair).

Evaluation of Best Overall Response

The best overall response is the best response recorded from the start of the treatment until disease progression/recurrence (taking as reference for PD the smallest measurements recorded since the treatment started). In general, the patient's best response assignment will depend on the achievement of both measurement and confirmation criteria.

Table 7-2: Response Assessment by RECIST

Target lesions	Non-Target lesions	New Lesions	Overall response
CR	CR	No	CR
CR	Incomplete response /SD	No	PR
PR	Non-PD	No	PR
SD	Non-PD	No	SD
PD	Any	Yes or No	PD
Any	PD	Yes or No	PD
Any	Any	Yes	PD

Patients with a global deterioration of health status requiring discontinuation of treatment without objective evidence of disease progression at that time should be classified as having “symptomatic deterioration”. Every effort should be made to document the objective progression even after discontinuation of treatment.

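### Lost patients are censored for PFS at last contact rather than last tumour assessment, so phone-only time after scanning stops counts as progression-free

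*Combined protocol and SAP*

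**What the plan says.** Section 7.4 names response rate and PFS as the primary endpoints, then gives one censoring date for both efficacy and survival: "Patients who are lost to follow-up will be censored as of the last official contact date for efficacy and survival outcome analysis". No other section gives a PFS censoring rule or refers to the last evaluable scan. Section 9 names Kaplan-Meier for time to progression and overall survival but adds no rule.

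Imaging follows treatment. Section 7.4: "Tumor response assessment will be performed after every two cycles of therapy using cross-sectional imaging according to the RECIST 1.1 criteria". Section 4: "One cycle will be defined as 4 weeks". Scans are therefore 8 weeks apart while therapy continues. In Table 7-1, as far as the extracted layout shows, the MRI/CT row is marked at screening, C3D1, C5D1 and from C7D1 on, and is blank under End of Study and Follow-up.

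Contact continues after treatment. Under section 4.2 all patients are to be "contacted for survival follow-up at least monthly via phone or office visit until death or the completion of the trial". For those who stop because of side effects: "Patients who discontinued therapy for reason of toxicity will be monitored at least monthly via phone or office visit until resolution of the adverse event".

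The nearest thing to a safeguard is in the response criteria of section 7.4: "Every effort should be made to document the objective progression even after discontinuation of treatment". It concerns patients classed as having symptomatic deterioration, and it sets no schedule.

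**The concern.** A phone call can establish that a patient is alive. It cannot establish that RECIST progression is absent. In a Kaplan-Meier analysis, a patient who remains in the risk set after the last scan enlarges the denominator but can no longer contribute a detected progression. The estimated hazard falls and the PFS curve rises.

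An example: a patient is scanned at week 16, stops for toxicity without progression, is phoned until week 43 and is then lost. Under the stated rule, 43 - 16 = 27 unscanned weeks count as progression-free, although the scans that continued treatment would have brought at weeks 24, 32 and 40 never took place.

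The 1-year PFS rate estimates a primary endpoint and is judged against a 50% activity threshold. It also chooses the winner when response rates are identical or no arm has 3 responses (sections 4 and 9.1).

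**Working it through.** **1. The plan's own figure.** Sections 4 and 9.1 give 28 patients per arm, 20% against 50% at 1 year, and power 0.95; Figure 4-1 gives a two-sided alpha of 0.05. One-sample normal approximation:

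power = Φ[(√28 × 0.30 - 1.96 × √(0.2 × 0.8)) / √(0.5 × 0.5)] = Φ[(1.587 - 0.784) / 0.5] = Φ(1.607) = 0.946.

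This agrees with 0.95. The censoring rule does not alter the design figures; it alters the estimate.

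**2. Closed-form illustration.** Assume exponential PFS with median 9 months, the lower end of the range cited in section 9.1. Then S(4) = 2^(-4/9) = 0.735, S(12) = 2^(-12/9) = 0.397 and S(12 given 4) = 2^(-8/9) = 0.540. Suppose 10% of those progression-free at month 4 (0.735 × 0.10 = 7.4% of the arm) are never scanned again, are phoned past month 12 and are then lost.

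- Last-contact censoring: 0.735 × (0.10 + 0.90 × 0.540) = 43.1%.
- Last-scan censoring: 0.735 × 0.540 = 39.7%, the true rate.

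The mechanism is confirmed, but this case is near the worst: everyone affected stops early and stays reachable past a year.

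**3. Simulation with stopping times spread over the year.** Exponential PFS, scans every 8 weeks, Kaplan-Meier at 12 months. A share q of patients is given a stopping time uniform over 0 to 12 months, has no scan after it, is reached by phone for G months and is then lost. Both q and G are assumptions. Some of these patients progress before their stopping time, so the share that actually leaves without detected progression is smaller: 2.8% or 3.8% of the arm for q = 5%, and 11.2% or 15.1% for q = 20% (true rates 20% and 50%).

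Excess of last-contact over last-scan censoring, in percentage points (true 1-year rate 20% / 50%):

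| q | G = 0 | G = 3 | G = 6 | G = 12 |
|---|---|---|---|---|
| 5% | 0.0 / 0.0 | 0.5 / 0.4 | 1.0 / 0.8 | 1.7 / 1.1 |
| 10% | 0.0 / 0.0 | 1.0 / 0.9 | 2.1 / 1.7 | 3.3 / 2.3 |
| 20% | 0.0 / 0.0 | 2.2 / 1.9 | 4.3 / 3.4 | 6.7 / 4.7 |

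Last-scan censoring matched the estimate with no loss, within simulation error, in every scenario. G = 0 stands for patients lost while still on the scan schedule. No progression can be recorded between scans, so the two rules agree.

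**4. Effect on the 50% threshold.** With n = 28, a true rate of 40% and G = 6 months, the chance that the estimate reaches 50% is:

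- q = 20%: 37% under last contact, 24% under last scan, 28% with no loss.
- q = 5%: 29% under last contact, 25% under last scan, 28% with no loss.

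**5. Deaths.** The simulation ignores deaths in the phone period, which monthly contact would pick up as PFS events. Section 9.1 cites 90% alive at 1 year, so deaths would reveal few of the missed progressions.

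**The case against.** The strongest objection is scope. The rule covers patients who are lost. To be affected, a patient must stop scanning without progression, be phoned for months, and only then be lost. A reader might infer that everyone off treatment and still reachable is counted as progression-free to the last call. The documents do not say so; they state no PFS censoring date for that group. This stands. It narrows the point, and it shows a second gap that the same sentence should close.

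Size is the next objection. The only related figure is the estimate in section 7.4 that about 5% will be inevaluable, which is not a loss rate for PFS. At that level the bias is below 2 points. The standard error with 28 patients and a true rate of 39.7% is √(0.397 × 0.603 / 28) = 9.2 points. This stands too, although a systematic upward shift is not excused by being smaller than the random error.

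A reader might also infer that the bias favours the more toxic arm. The documents do not establish this. Patients who stop for drug-related toxicity before a restaging scan are replaced, those who stop for symptomatic progression before a scan count as progressed, and later toxicity stops are not lost while they are being monitored.

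Finally, last-scan censoring is unbiased only if dropout is unrelated to prognosis. Suppose, as an illustration, that the 20% who leave scanning at month 4 then have twice the hazard. The true 1-year rate is 0.735 × (0.8 × 0.540 + 0.2 × 0.540²) = 36.0%, and last-scan censoring still gives 39.7%. Last-contact censoring, with calls past month 12, gives 0.735 × (0.2 + 0.8 × 0.540) = 46.5%. The recommended rule is imperfect but clearly the better one.

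**Conclusion.** The point holds for patients who leave treatment and scanning without progression, remain in phone contact and are later lost. For them the stated rule counts unobserved time as progression-free, and no other section corrects it. The direction is upward. The size depends on quantities the documents do not give: about 0.4 to 1.7 points at an assumed 5% share and about 2 to 7 points at 20%, with 3 to 12 months of phone-only contact, exponential PFS and dropout unrelated to prognosis. I am confident of the direction, not of the size.

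It would be too strong to say that the rule generally decides the trial. Response rate is applied first, and 1-year PFS selects an arm only in the two fallback situations. It remains a primary endpoint, so its estimate matters in its own right. This deserves correction before analysis but does not undermine the design.

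**What to change.** In sections 7.4 and 9:

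- For every patient without documented progression or death, censor PFS at the last adequate tumour assessment without progression, or at day 1 if there is no post-baseline scan. This also covers patients who are off treatment but still reachable.
- Keep the last contact date for overall survival only.
- Report PFS with last-contact censoring as a sensitivity analysis.

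The cost is a few sentences. Scan dates are already collected, and the 28 per arm and stated power are unchanged. The downsides are slightly less follow-up time and continued reliance on dropout being unrelated to prognosis. Continued scans until progression in patients who stop without it would address that second weakness. They are worth considering, but they would add imaging and are not needed for the wording change.

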The investigational agents in this trial have not been previously studied in thyroid cancer, therefore we are unable to accurately determine the patient drop-off rate. Nonetheless, we have estimated that approximately 5% of all enrolled patients will be deemed inevaluable for safety and or efficacy assessment due to various factors listed above.

Tumor response

Response assessment will be based on the RECIST 1.1 criteria. Only patients with measurable disease at baseline should be included in the study.

Definitions

Measurable Disease - the presence of at least one measurable lesion. If the measurable disease is restricted to a solitary lesion, its neoplastic nature should be confirmed by cytology/histology.

Measurable Lesions - lesions that can be accurately measured in at least one dimension with longest diameter ≥ 20 mm using conventional techniques or ≥ 10 mm with spiral CT scan.

Non-measurable Lesions - all other lesions, including small lesions (longest diameter < 20 mm with conventional techniques or < 10 mm with spiral CT scan), i.e., bone lesions, leptomeningeal disease, ascites, pleural/pericardial effusion, inflammatory breast disease, lymphangitis cutis/pulmonis, cystic lesions, and also abdominal masses that are not confirmed and followed by imaging techniques; and:

All measurements should be taken and recorded in metric notation, using a ruler or calipers. All baseline evaluations should be performed as closely as possible to the beginning of treatment and never more than 4 weeks before the beginning of the treatment.

The same method of assessment and the same technique should be used to characterize each identified and reported lesion at baseline and during follow-up.

Clinical lesions will only be considered measurable when they are superficial (e.g., skin nodules and palpable lymph nodes). For the case of skin lesions, documentation by color photography, including a ruler to estimate the size of the lesion, is recommended.

Methods of Measurement

- CT and MRI are the best currently available and reproducible methods to measure target lesions selected for response assessment. Conventional CT and MRI should be performed with cuts of 10 mm or less in slice thickness contiguously. Spiral CT should be performed using a 5 mm contiguous reconstruction algorithm. This applies to tumors of the chest, abdomen and pelvis. Head and neck tumors and those of extremities usually require specific protocols.

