- ii. Documentation of the qualifications, training and experience of the PI and other study staff
- iii. Eligibility of consented/enrolled patients
- iv. Informed consent document and process
- v. Verification that the local PI and staff are performing trial functions in accordance with protocol
- vi. Accuracy, completeness and timeliness of data
- vii. Accuracy and completeness of all source documentation
- viii. Response evaluation: verify that responses are identified according to the protocol definition of response for any response that is a major endpoint
- ix. Toxicity
- x. Appropriate reporting of all AEs and SAEs as required by GCP, the protocol, IRB regulations, sponsor's SOPs and other regulatory requirements

The monitor shall meet with RN/Coordinator assigned to the trial to:

provide an itemized review of the deficiencies to the RN/Coordinator and remove items from itemized review which are corrected during this meeting

review and document corrections; the RN/coordinator should indicate any remaining deficiencies and provide corrective action plan for resolution

prepare summary report for PI and Monitoring Committee to include summary of systematic deficiencies, significant protocol deviations, summary of remaining deficiencies and RN/coordinator corrective action plan, recommendations for data collection, protocol revision for clarity

The Monitor shall meet with the overall PI to discuss the report and document the PI's responses prior to submitting final report to the Monitoring Committee

The final Monitoring Committee review of audit report and PI response and PI summary of protocol to date will be included in the annual renewal submission.

Egregious data insufficiencies that may impact the scientific integrity of the trial are reported to the Medical Director and Clinical Trial Review Committee.

Please see the attached supplementary Emory University WINSHIP CANCER INSTITUTE data safety monitoring plan policy document for a complete detail of the monitoring plan.

9 Statistical methods and data analysis

All treated subjects will be included in the analysis of efficacy and safety.

Demographic and baseline characteristics will be summarized using descriptive statistics. The toxicities will be tabulated by organ system. Time to disease progression and overall survival will be evaluated using the Kaplan-Meier method.

Correlative analysis will be exploratory in the context of this Phase II screening trial.

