Between Arms: Any treatment arm closed to accrual after the first stage interim analysis will be considered an inferior arm and will be excluded from comparison for the winner of trials. The arm with the best overall RR at the end of full enrolment will be adjudged the winner to be considered for further development provided there are at least 3 objective responses. Only in the event of identical RR between 2 or more arms or if none of the arms met the RR criterion (less than 3 objective responses after full patient enrolment) would the 1-yr PFS rate be employed to determine a winner. Based on recent clinical trials of targeted agents in similar patient population, 90% of patients were alive at 1 year and median progression free survival ranged between 9 and 18 months.⁸⁻¹⁰ We assume a conservative estimate that only 20% of the patients will be progression free at 1 year if the treatment is ineffective while 50% or more of the patients will be progression free at the same time point with an effective regimen. For this purpose, a 1-year PFS rate of 50% or greater will be considered sufficient activity to justify further evaluation of the treatment in this disease. Assuming a 20% or lower 1-year PFS rate with an inactive regimen and a 50% or greater rate with an active regimen, 28 patients enrolled onto each arm will classify the treatment as having sufficient activity for further evaluation with a probability of 0.95 (power against the alternative hypothesis $p = 0.05$). In this respect, the arm with the highest 1-yr PFS rate will be judged the winner. In the event of a tie between the arms for both the RR and 1-yr PFS rate, the arm with the best profile in terms of safety and tolerability will be considered the overall winner to be selected for further evaluation in this disease. The power calculation for PFS assessment assumes full enrolment of 28 patients to the treatment arm, therefore any arm closed to further accrual following the initial interim analysis will not be eligible for the PFS endpoint assessment. The investigational agents in this trial have not been previously studied in thyroid cancer; therefore we are unable to accurately determine the drop-off rate. Nonetheless, all patients

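### The safety tie-break that picks the winner does not count patients who stopped early for drug toxicity, which biases it toward an arm with more such stops

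*Combined protocol and SAP*

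**What the plan says.** Sections 4 and 9.1 choose the winner in steps: response rate (RR) first, then the 1-year PFS rate. If arms tie on both, "the arm with the best profile in terms of safety and tolerability will be considered the overall winner".

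Section 7.4 sets the population for that last step. In the sentence that opens with *Notwithstanding*, it says that "only patients who are evaluable for the primary efficacy endpoint may be included in the safety assessment" made to pick the winner.

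The same section defines who is evaluable:
- "All patients who completed at least 2 cycles of therapy will be deemed evaluable for the efficacy endpoint". Section 4 makes a cycle 4 weeks, with imaging at the end of every even-numbered cycle.
- If a patient stops before two cycles "for reasons other than disease progression, the affected subject will be considered inevaluable for efficacy and will be replaced by another subject" on the same arm.
- "Patients who discontinue treatment due to drug-related toxicity prior to obtaining a restaging scan would be considered inevaluable and would be replaced".
- Patients who stop for symptomatic progression before a scan count as progressed and are not replaced.

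For overall safety, Section 7.4 uses a different set: "Patient will be evaluable for overall toxicity and safety endpoint determination if they received any dose of the investigational agent". The opening of Section 9 states without exception: "All treated subjects will be included in the analysis of efficacy and safety".

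Section 7.4 also estimates that "approximately 5% of all enrolled patients will be deemed inevaluable for safety and or efficacy assessment". No toxicity measure is named for the tie-break.

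**The concern.** A comparison of safety and tolerability should not drop patients because of a safety outcome. Here, stopping early for drug toxicity is itself what removes a patient from the comparison. The replacement patient enters the denominator, and the toxicity that ended the first patient's treatment is counted nowhere in that step.

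The arms are two different single agents and their combination, so early toxicity stopping may well differ between them. If it does, the rule favours the arm with more of it. What is at stake is the choice of regimen for further development when efficacy does not separate the arms, which is exactly when tolerability ought to decide.

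**Working it through.** **Inputs from the documents**
- Evaluable per arm: 18 + 10 = 28 (Sections 4 and 9.1).
- Enrolled per arm: 30, or 90 in total (Section 5).
- Expected inevaluable: about 5% (Section 7.4), so 30 × 0.05 = 1.5 patients per arm.
- RR design: 5% v 15%, power 80%, α 0.20 (Figure 4-1).

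**The plan's own figures.** An exact minimax search returns the stated design: stop at 0 of 18, reject at 2 or fewer of 28. Exact α is 0.158 and power 0.803. For enrolment, 28/0.95 = 29.5, which rounds up to 30 per arm, and × 3 = 90. The planned margin for replacement is thus 30 − 28 = 2 patients per arm. The documents attach no figure to the safety tie-break itself, so every toxicity rate below is an assumption.

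**Example at the planned size**, taking each early toxicity stop as a severe toxicity:

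| | Arm X | Arm Y | Looks safer |
|---|---|---|---|
| Evaluable only | 9/28 = 32.1% | 8/28 = 28.6% | Y |
| Replaced for early toxicity | 0 | 2 | |
| All treated | 9/28 = 32.1% | (8+2)/(28+2) = 10/30 = 33.3% | X |

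**When the expected ranking reverses.** Let q be the true severe-toxicity rate among all treated patients and s the share who stop early for toxicity. The rate among evaluable patients is (q − s)/(1 − s). If X has no early toxicity stops, Y falls below X once s exceeds (qY − qX)/(1 − qX). With 28 evaluable patients, that share corresponds to 28/(1 − s) − 28 early stops.

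| Assumed qY v qX | Threshold for s | Early stops in Y |
|---|---|---|
| 33% v 30% | 0.03/0.70 = 4.3% | 28/0.957 − 28 = 1.3 |
| 35% v 30% | 0.05/0.70 = 7.1% | 28/0.929 − 28 = 2.2 |
| 40% v 30% | 0.10/0.70 = 14.3% | 28/0.857 − 28 = 4.7 |

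So a margin of about 2 replacements can reverse a close comparison. A 10-point difference needs about 5.

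**Chance of ranking the more toxic arm as safer.** Simulation with 400,000 trials per row, 40% in Y v 30% in X, no early toxicity stops in X:

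| Early toxicity stops in Y | Y's rate among evaluable | Y looks safer, evaluable set | Y looks safer, all treated |
|---|---|---|---|
| 5% | 0.35/0.95 = 36.8% | 24.5% | 20.4% |
| 10% | 0.30/0.90 = 33.3% | 33.9% | 20.9% |
| 15% | 0.25/0.85 = 29.4% | 46.1% | 20.9% |
| 20% | 0.20/0.80 = 25.0% | 60.7% | 20.8% |

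If both arms have 5% early toxicity stops, the evaluable rates are 0.25/0.95 = 26.3% for X and 36.8% for Y. The order is kept.

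**How often the step is reached.** For one pair of arms with equal true rates, counting 1-year PFS as a binomial in 28 patients and treating the two ties as independent:
- At 15% RR and 50% PFS: 0.150 × 0.106 = 1.6%.
- At 5% RR and 20% PFS: 0.256 × 0.133 = 3.4%, before allowing for stage I closure, which lowers it.

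**The case against.** The strongest reply is that this seldom matters. The step needs ties on both RR and 1-year PFS rate, Section 4 calls the study non-comparative, and Section 9.2 also brings in the clinical benefit rate as a further reference. Anyone given a dose remains in the overall safety report, and the monitoring committee sees safety data, so early toxicity would be visible to those deciding. At the expected 5% inevaluable from all causes, only close comparisons would flip. All of this stands, and it limits the weight of the point. It does not make the stated rule sound: the overall report is not what the rule uses to name the winner, and Section 7.4 admits that the drop-off rate cannot be accurately determined.

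The second reply is that *Notwithstanding* shows a deliberate exception, so Sections 7.4 and 9 can be read as general rule and carve-out. That reading is fair. The sections still need reconciling, because Section 9 states its rule without exception, and intent does not remove the bias.

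Three stronger readings are tempting, and the documents do not support them:
- *The rule removes exactly the patients with the worst tolerability.* It removes stops before the first scan or before two cycles. Later toxicity stops, and severe events in patients who continue, stay in. Early withdrawals and losses to follow-up unrelated to toxicity are also removed.
- *The more patients an arm loses early to toxicity, the better it looks.* With the results in evaluable patients fixed, further early stops leave the arm's figure unchanged. They go unpenalised. The figure falls only in the sense that, for a given overall toxicity rate, more of the toxicity lies outside the set.
- *The step gives the wrong answer whenever it is used.* It uses the wrong population, but the ranking changes only when early toxicity stopping differs enough between arms.

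**Conclusion.** The flaw is real and of low frequency. Under the rule as written, early toxicity stops do not count against an arm in the safety comparison that can name the winner, and no other section undoes this. Two replaced patients, the plan's own per-arm margin, are enough to reverse a close comparison. A 10-point difference in true severe toxicity reverses in expectation only if more than about 14% of the worse arm stops early for toxicity and none of the other arm does.

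These sizes rest on assumed toxicity and early-stop rates, on treating each early stop as severe, and on a severe-toxicity proportion as the measure, which the plan does not specify. Unequal early stopping between these arms is plausible but undocumented. The renal cancer figures in Section 6.7 (7% v 0% permanent discontinuation for adverse reactions on everolimus v placebo) cover stops at any time and do not compare these arms.

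The effect of the same replacement rule on the RR denominator is a separate question.

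**What to change.** - Delete the *Notwithstanding* sentence in Section 7.4. Run the tie-break on all patients who received any dose of study drug, in line with that section's any-dose safety rule and the all-treated statement opening Section 9.
- Count each discontinuation for drug-related toxicity before the first scan as a tolerability failure.
- Name the toxicity measure for the tie-break in advance. Otherwise the step in Sections 4 and 9.1 still cannot be reproduced.
- As an addition that Section 9 does not contain, attribute events to the randomised arm and count only those before any switch to the combination (Arms A1 and B1).

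The cost is one deleted sentence and a few lines of definition. No new data or patients are needed, because toxicity is already recorded for everyone dosed.
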